8.3.4. Immunoglobulin Reference Range Shifts from Baseline by Visit

For immunoglobulins (IgA, and IgM) reference range shifts will be summarized across all visits based on the baseline normal range category. For subjects with immunoglobulin values below the LLN, the number and percentage of subjects who 'remained low' or went 'to normal/high' post-baseline will be summarized. Similarly, for subjects with immunoglobulin values within the normal range or above the ULN, the number and percentage of subjects who 'remained normal/high' or went 'to low' post-baseline will be summarized. This analysis will be performed for Year 1 and Year 1&2 separately [T13.77, T23.71].

8.3.5. Worst Laboratory Toxicity Grade Post-Baseline

Laboratory toxicity will be graded using grades corresponding to mild, moderate, severe, and life-threatening when possible. The worst laboratory toxicity grade for each laboratory parameter within each laboratory category (hematology, liver function, electrolytes, other chemistries, urinalysis and immunoglobulins) during Year 1 and Year 1&2 separately will be presented. Data for both scheduled and unscheduled visits will be included. For calcium, sodium, potassium and glucose, grades associated with hypo- and hyper- conditions will be included [T13.56, T13.60, T13.64, T13.68, T13.71, T13.75, T23.50, T23.54, T23.58, T23.62, T23.65, T23.69].

8.3.6. Immunoglobulin Below LLN by Visit

The number and percentage of subjects with immunoglobulin values (IgG, IgA, and IgM) below the LLN at each visit will also be presented for all subjects and then repeated for subjects \geq LLN at baseline for Year 1 and Year 1&2 separately. No statistical test will be performed [T13.78, T13.79, T23.72, T23.73].

8.3.7. Immunoglobulin Relative to LLN by Visit

The number and percentage of subjects with immunoglobulin values (IgG, IgA, and IgM) greater than or equal to the LLN at each visit will also be presented for all subjects and then repeated for subjects $<$ LLN at baseline for Year 1 and Year 2 separately. No statistical test will be performed [T13.80, T13.81, T23.74, T23.75].

8.3.8. Immunogenicity

For the immunogenicity assessment for belimumab, two types of antibody assays will be performed, i.e. a binding assay and neutralizing assay. For the immunogenicity assessment for rituximab only a binding assay will be performed. For the binding assay, there will be 3-testing steps. A screening assessment is performed which produces a result of positive or negative. Confirmed positive samples will be further characterised for a relative level of binding (titre value). Subjects will be viewed as positive for anti-drug antibody (ADA) if the confirmation assay is positive. Subjects, who confirm positive in the anti-belimumab ADA assay, will be evaluated for the presence of neutralising antibody (Nab) response with the NAb assay, which again produces a result of positive or negative.

For incidence of subjects with positive binding antibody during the study period, a table will be produced summarizing results for the binding antibody assay by treatment group and visit. The table will include the number and proportion of subjects in each results category for each visit in the study period (including early withdrawal visit). Binding confirmatory assay results will be categorized as negative, persistent positive (defined as a positive immunogenic response at least two consecutive assessments during the study period or a single result at the final assessment in the study period) or transient positive (defined as a single positive immunogenic response that does not occur at the final assessment in the study period).

Results will be summarized by visit and by treatment group for belimumab (Year 1 and Year 2, separately) and for Arms A and B only for rituximab (Year 1) [T13.82 T13.83, T23.76]. A listing of immunogenicity results will also be presented [L13.33, L23.33].

8.3.9. Further Research Samples

Blood leukocyte analysis and B cell receptor samples collected at selected sites in the USA will be reported separately and are not considered in this RAP.

B Cell subsets collected at selected sites in the European Union (EU) will be reported separately and are not considered in this RAP.

8.4. Other Safety Analyses

The analyses of non-laboratory safety test results including vital signs will be based on GSK Core Data Standards, unless otherwise specified.

8.4.1. Vital Signs

A summary of vital signs and change from baseline in vital signs will be presented by visit for Year 1 and Year 2 separately. Weight will be included in these summaries [T13.84, T13.85, T23.77, T23.780].

8.4.2. Neurological Assessment

Findings consistent with the diagnosis of Progressive Multifocal Leukoencephalopathy (PML) will be recorded as adverse events.

9. HEALTH OUTCOMES ANALYSES

Health outcomes reporting will be conducted on the MITT population, following the principles of the Efficacy analysis.

Additional details for the Health Outcome scales are provided in the appendix: Lupus QoL (Section 15.6.10); WPAI (Section 15.6.11); FACIT-Fatigue Scale (Section 15.6.12).. A listing of all health outcomes endpoints will be presented [L24.01-L24.03].

Exit interviews assessing patients experience of the clinical trial will be databased and reported separately.

The Health Outcome scales are completed by the subject and are very subjective, therefore, all data after the COVID-19 environment onset date (Section 15.6.16) is very likely to be either missing due to the pandemic or affected by the pandemic. It is also expected that the Health Outcomes data collected at different stages of the COVID-19 pandemic may be affected in different ways. As per the second additional analysis for the primary Efficacy endpoint, there may be intangible ways that the data may have been affected even if it has been collected, therefore we cannot distinguish between affected and unaffected data after the COVID-19 environment onset date.

For these reasons, additional analyses defined below have been added for Week 52 and Week 64. A hypothetical strategy was already proposed to deal with missing data due to study withdrawal and this has been expanded to also define the COVID-19 environment onset date as an Intercurrent Event for any subject who has their (scheduled) Week 52 (or Week 64) assessment on or after the onset date. The data for these subjects will be treated as missing values and will be assumed to be Missing At Random (MAR). It will be imputed using Multiple Imputation methods, which take into account the subjects baseline characteristics and their existing pre-COVID data.

The analysis for Week 104 has not been modified as all observed Week 104 data will be collected after the COVID-19 environment onset date, so the Multiple Imputation approach will not be possible. This means that the results should be interpreted with caution.

Additional post-SAC analyses may be carried out to assess the impact of the COVID-19 pandemic on the Health Outcomes data.

9.1. Statistical Methodology Specification for Continuous Endpoints

| Endpoints |
|--|
| 
For all reported timepoints upto Week 52 (Year 1 reporting) and upto week 104 (Year 2 reporting):
 
Patient Global Assessment (PtGA) of Disease Activity
 
 • Change from baseline in PtGA by visit [T14.01, T24.01]. |

| |
|---|
| 
LupusQoL Domain Scores
 
 • Change from baseline in each of the 8 LupusQoL Domain scores by visit [T14.02, T24.02]. 
FACIT-Fatigue Scale Score
 
 • Change from baseline in FACIT-Fatigue Scale score by visit [T14.03, T24.03]. 
Work Productivity and Activity Impairment (WPAI)
 
 • Change from baseline in WPAI percent overall work productivity impairment by visit [T14.05, T24.05]. • Change from baseline in WPAI percent activity impairment score by visit [T14.06, T24.06]. |
| 
Derivation
 |
| 
Derivation of the endpoints is provided in Section 15: Lupus QoL (Section 15.6.10); WPAI (Section 15.6.11); FACIT-Fatigue Scale (Section 15.6.12).
 |
| 
Strategy for Intercurrent (Post-Randomization) Events
 |
| 
A hypothetical strategy will be used to estimate what the treatment effect would have been had the subjects not had missing data.
 |
| 
Imputation of Data for Missed Visits, and Following Study Withdrawal
 |
| 
 • A bayesian repeated measures normal model will be fitted to the observed data, using a Markov Chain Monte Carlo approach, adjusting for treatment group, baseline SLEDAI-2K score (≤ 9 vs. ≥ 10), baseline immunosuppressant use (use vs. non-use), and baseline corticosteroid dose (prednisone equivalent ≤ 10 mg/day vs. > 10 mg/day). Non-informative priors will be used • Quasi-independent samples will be drawn from the posterior distributions for the parameters of the multivariate normal distribution for each treatment group and each missingness pattern. • Each sample leads to a separate imputed dataset, in which the missing values are replaced by values drawn randomly from their conditional distribution. This distribution is based on the observed data and the covariates for that subject using the imputation model and the sampled parameter values. • 
These steps will be repeated at least 1000 times.
 |
| 
Model Specification
 |
| 
 • Each imputed dataset will be analyzed using ANCOVA to evaluate the treatment effect controlling for treatment group, baseline SLEDAI-2K score (≤ 9 vs. ≥ 10), baseline immunosuppressant use (use vs. non-use), and baseline corticosteroid dose (prednisone equivalent ≤ 10 mg/day vs. > 10 mg/day) and baseline value. • The resulting treatment differences and their SEs will be combined across imputations using Rubin's rules. |

| |
|--|
| Model Checking & Diagnostics |
| The Kolmogorov-Smirnov D statistic will be used to test the assumption of normality. Residuals will be reviewed to assess the homogeneity of variance assumption. |
| Model Results Presentation |
| 
The tables will display:
 
 • Baseline: the number subjects, mean, standard error, standard deviation, median, 25th percentile, 75th percentile, minimum, maximum for each arm • At each visit: 
 ○ the number subjects, mean, standard error, standard deviation, median, 25th percentile, 75th percentile, minimum, and maximum ○ LS Mean, and standard error of the LS Mean for each arm at Weeks 52, 64 and 104. ○ the treatment difference and 95% confidence interval (CI) for the comparison of Arm B vs Arm A; and Arm B vs Arm C at Weeks 52, 64 and 104. ○ the p-value for treatment difference for Arm B vs Arm A at Weeks 52, 64 and 104. |

9.1.1. Additional Analyses to Assess the Impact of the Coronavirus Disease 2019 (COVID-19) Pandemic (Continuous Endpoints upto Week 52 and Week 64)

The analysis will be repeated, but visits that were conducted on or after the COVID-19 environment onset date (Section 15.6.16) will be considered as impacted and hence removed from the analysis, as if the subjects had withdrawn.

A hypothetical strategy will be used to estimate what the treatment effect would have been had the subjects not had missing data (including the missing data from the removal of impacted COVID-19 visits). Weeks 72 and 104 are anticipated to have too much data post the COVID-19 environment onset date and hence will not be included.

Patient Global Assessment (PtGA) of Disease Activity

- Change from baseline in PtGA by visit [T14.08,T24.08].

LupusQoL Domain Scores

- Change from baseline in each of the 8 LupusQoL Domain scores by visit [T14.09,T24.09].

FACIT-Fatigue Scale Score

- Change from baseline in FACIT-Fatigue Scale score by visit [T14.10,24.09]

Work Productivity and Activity Impairment (WPAI)

- Change from baseline in WPAI percent overall work productivity impairment by visit [T14.12, 24.12].
- Change from baseline in WPAI percent activity impairment score by visit [T14.13, 24.13].

For change from baseline endpoints, a plot of LS means +/- SE by visit and treatment group will be provided.[Year 1: F14.01, Year 1 and 2 combined, but only up to Week 64: F24.01-24.06].

9.2. Statistical Methodology Specification for Proportion Endpoints

| |
|--|
| Endpoint / Variables |
| 
 The proportion of participants with an improvement in FACIT-fatigue score exceeding the minimal clinically important difference (MCID is ≥ 4) by visit. |
| Derivation |
| Derivation of the FACIT endpoint is provided in Section 15.6.12. A subject is considered to have an improvement exceeding the minimal clinically important difference if they have ≥ 4 points improvement in their FACIT-Fatigue Scale score from baseline. |
| Imputation of Data for missed visits, and following study withdrawal.. |
| Missing Data will be imputed as detailed in Section 9.1.1, then categorized as Responder/Non-Responder using the derivation above. For consistency of results, the same seed will be used for the imputation of missing data on the continuous FACIT scale and the imputation on the continuous scale that is then dichotomized into the binary response. |
| Model Specification |
| 
 Each imputed dataset will analyzed using the proposed statistical analyses planned for the primary endpoint. The FACIT-fatigue score at baseline will also be included as a covariate. The resulting Odds Ratios and their SEs will be combined across imputations using Rubin's rules. |
| Model Checking & Diagnostics |
| 
 The model and diagnostics checks proposed for the primary endpoint will be repeated for this endpoint. |
| Model Results Presentation |
| 
 For each endpoint a table [T14.04, T24.04]. will display: 
 the number, percentage, SE of percentage, and the 95% CI for the percentage of subjects achieving a response by treatment group, the observed difference in percentage of responders for the comparison of Arm B vs Arm A; and Arm B vs Arm C, the odds ratio and 95% confidence interval (CI) for the comparison of Arm B vs Arm A; and Arm B vs Arm C at Weeks 52, 64 and 104. the p-value for the odds ratio the treatment difference for Arm B vs Arm A at Weeks 52, 64 and 104. |

9.2.1. Additional Analyses to Assess the Impact of the Coronavirus Disease 2019 (COVID-19) Pandemic

The analysis will be repeated however visits that were conducted on or after the COVID-19 environment onset date (Section 15.6.16) will be considered as impacted and hence removed from the analysis, as if the subjects had withdrawn.

A hypothetical strategy will be used to estimate what the treatment effect would have been had the subjects not had missing data (including the missing data from the removal of impacted COVID-19 visits). Weeks 72 and 104 are anticipated to have too much data post the COVID-19 environment onset date and hence will not be included.

The proportion of participants with an improvement in FACIT-fatigue score exceeding the minimal clinically important difference (MCID is ≥ 4) by visit [T14.11, T24.11].

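### SAP Section 9.2 cites the COVID-19 additional analysis (9.1.1) for imputing the main FACIT-Fatigue responder endpoint, where Section 9.1 is probably meant

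*SAP*

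**What the plan says.** Four adjoining subsections of the SAP are involved.

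- **Section 9.1** is the main analysis of the continuous patient-reported scores, including FACIT-Fatigue. It holds the imputation model: a Bayesian repeated-measures normal model, fitted by MCMC to all observed data and used to fill missed visits and visits after withdrawal. Results are due at Weeks 52, 64 and 104.
- **Section 9.1.1** repeats that analysis to assess COVID-19. Its title limits it to "Continuous Endpoints upto Week 52 and Week 64". Visits from the onset date onward "will be considered as impacted and hence removed from the analysis, as if the subjects had withdrawn", and its missing data are defined as "including the missing data from the removal of impacted COVID-19 visits". It adds: "Weeks 72 and 104 are anticipated to have too much data post the COVID-19 environment onset date and hence will not be included".
- **Section 9.2** is the main FACIT responder analysis. Under a row titled "Imputation of Data for missed visits, and following study withdrawal" it says: "Missing Data will be imputed as detailed in Section 9.1.1", after which each imputed score is classed as response or non-response. It then asks for one seed across the continuous and dichotomised FACIT imputations. Among its results is "the p-value for the odds ratio the treatment difference for Arm B vs Arm A at Weeks 52, 64 and 104".
- **Section 9.2.1** repeats the responder analysis with post-onset visits removed and, again, without Weeks 72 and 104 (T14.11, T24.11).

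The opening of Section 9 presents the COVID-19 analyses as additions for Weeks 52 and 64. It says the Week 104 analysis is unchanged, because all observed Week 104 data will fall after onset and multiple imputation could not be done there. The October 2020 and July 2021 addenda leave the reference in Section 9.2 as it is. The July 2021 addendum keeps T24.04 as a Year 1 and 2 output.

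**The concern.** The reference sends the reader to a subsection whose content is a rule for removing data, not a method for imputing it. A programmer who applies Section 9.1.1 in full would build the main responder table on pre-onset visits only.

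The main table and its COVID-19 counterpart would then rest on the same data, so comparing them would say nothing about the pandemic. The responder and continuous FACIT results would come from different inputs, although the plan wants them to agree. Section 9.2 would also be asking for Week 104 results under a rule that excludes Week 104.

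The endpoint is a protocol secondary endpoint. In the abridged end-of-study list T24.04 is its only inferential table; the other planned display is a figure of observed data.

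**Working it through.** The plan states no figure to reproduce here, because the point is a cross-reference. The check sets the four subsections side by side and then works out which visits a literal reading would remove.

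**Step 1: the subsections compared.**

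| | 9.1 | 9.1.1 | 9.2 | 9.2.1 |
|---|---|---|---|---|
| Role | Main, continuous | COVID-19 repeat of 9.1 | Main, FACIT responder | COVID-19 repeat of 9.2 |
| Observed post-onset visits | Kept | Removed | Not mentioned, except through the reference | Removed |
| Own imputation model | Yes | No | No; points to 9.1.1 | No |
| Week 104 | Reported | Excluded | Reported | Excluded |
| FACIT tables | T14.03, T24.03 | T14.10 in Year 1 | T14.04, T24.04 | T14.11, T24.11 |

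**Step 2: what follows if 9.2 takes its data rule from 9.1.1.**

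- *9.2 against 9.2.1.* Both would use pre-onset visits only, so they would agree at every visit up to Week 64. Year 1 reporting stops at Week 52, so T14.04 and T14.11 would be the same table.
- *9.2 against 9.1.* T14.03 would use all observed FACIT scores and T14.04 only the pre-onset ones. A shared seed cannot align imputations drawn from different data.
- *9.2 against itself.* Week 104 results are required, but the cited subsection excludes Week 104.

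**Step 3: which visits would be removed.** Onset dates are in SAP Section 15.6.16. Target study days are in Section 15.3.1: 365, 449 and 729 for Weeks 52, 64 and 104, that is 364, 448 and 728 days after first dose. A target visit is removed when first dose is on or after (onset date minus those days):

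| Country | Onset | Week 52 | Week 64 | Week 104 |
|---|---|---|---|---|
| Eight of the eleven | 10 Feb 2020 | 11 Feb 2019 | 19 Nov 2018 | 12 Feb 2018 |
| France | 25 Feb 2020 | 26 Feb 2019 | 4 Dec 2018 | 27 Feb 2018 |
| Canada | 10 Mar 2020 | 12 Mar 2019 | 18 Dec 2018 | 13 Mar 2018 |
| Russia | 13 Mar 2020 | 15 Mar 2019 | 21 Dec 2018 | 16 Mar 2018 |

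**Step 4: Week 104.** SAP Section 3.1 puts the first data monitoring meeting in September 2018, six months after the first randomisation, so that was about March 2018. Assume a date from 1 to 31 March 2018, with first dose the same day. The earliest Week 104 target is then 1 March 2018 + 728 days = 27 February 2020, or at the other end 31 March 2018 + 728 days = 28 March 2020. Even the earlier date is after onset everywhere except Canada and Russia. A visit 7 days early moves the limits only to 6 March 2018 (France), 20 March (Canada) and 23 March (Russia). Essentially no Week 104 visit precedes onset, in line with the opening of Section 9.

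**The case against.** The strongest reply is that this is a slip whose intent is plain, and most of that stands.

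- The row containing the reference concerns visits that were missed or came after withdrawal. Removing observed visits is a data-selection rule, not an imputation method.
- Section 9.1.1 has no model and simply repeats the analysis of Section 9.1. A reader who follows the reference only to find out how to impute arrives at the right model.
- Section 9.2.1 contrasts its removal of post-onset visits with Section 9.2, which makes sense only if Section 9.2 keeps them.
- The seed sentence ties the responder imputation to the continuous FACIT imputation, which Section 9.1 specifies in full.

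A reader might go further and infer that the plan throws away all observed post-onset FACIT data in its main responder analysis, that the two responder analyses are identical throughout, that T24.04 repeats T24.11, or that no Week 104 result can exist. The documents do not support these inferences. The context above points to post-onset visits being kept. Any match between Sections 9.2 and 9.2.1 ends at Week 64. T24.11 is absent from the abridged end-of-study list, so there is no such pair to duplicate. Section 9, Section 9.2 and the July 2021 addendum all leave Week 104 reporting in place.

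What does not stand is that an evident slip needs no correction. Section 9.1.1 counts the removed visits as missing data, so the literal reading is available to a programmer. The October 2020 addendum corrected slips of the same kind: it struck a mistaken term from another imputation description and reversed the terms of a duration formula.

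**Conclusion.** The reference in Section 9.2 is wrong as written and is probably meant to be Section 9.1. It is best described as a cross-reference inconsistency, not a chosen analysis. Its consequences are risks of a literal reading: loss of observed post-onset visits, a main table that coincides with its COVID-19 repeat up to Week 64, a mismatch with the continuous FACIT analysis, and a conflict over Week 104.

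The size is minor. The testing sequence covers only the primary and the two major secondary endpoints (SAP Section 5.6), so no confirmatory conclusion changes. The share of FACIT visits at risk cannot be calculated, because the documents give no enrolment by date; only the cut-off dates can be derived. Those dates rest on target visit days and, for Week 104, on the assumed March 2018 start.

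**What to change.** In Section 9.2, replace the reference to Section 9.1.1 with Section 9.1, and add one sentence stating that post-onset visits are removed only in Section 9.2.1. The main analysis then uses all observed FACIT data, imputes only missed and post-withdrawal visits from the same data as T14.03 and T24.03, and can report Weeks 52, 64 and 104.

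The cost is one corrected reference and one sentence in an addendum. No design figure, sample size or significance level changes. Where tables have already been programmed, check that T14.04 and T24.04 used the Section 9.1 inputs, and record the answer in the study report.

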9.3. Health Care Resource Utilization

The health care resource utilization (HCRU) data will be used to conduct exploratory economic analyses of:

- Number of outpatient/hospital clinic visits
- Number of emergency room/urgent care facility visits
- Number and duration of in-patient hospitalizations (total nights, including duration by wards [intensive care unit vs. general ward])
- Use of over the counter (non-prescription) medication.

These data will be provided by CRF Health, and planned analyses will be described in a separate document

A listing of data will be provided at Year 2 [L24.04]. Health care resource utilization will be summarised at Week 52 for Year 1 (T14.07), and at Week 104 for Year 1&2 (T24.07).

Duration of hospitalization will be summed for subjects with more than 1 hospitalisation. Subjects with ongoing hospitalization at Week 52 will be truncated for the Week 52 (Year 1) summary. Subjects with ongoing hospitalization at Week 104 will be truncated for the Week 104 (Year 2) summary at the last known date of hospitalization (i.e. including post study hospitalization if the hospitalization is ongoing at Week 104).

If subjects are withdrawing due to hospitalization then an additional exploratory analysis will be performed shortly after the Statistical Analysis Complete milestone.

